While some evidence supports the use of tissue adhesives for securement, further randomized controlled trials are needed to assess the effectiveness of this intervention. Further, only one prospective, randomized trial evaluated patients in the emergency room setting. Nearly 50% of all hospital admissions start in the emergency department (ED) and 80% of hospitalized patients require IV access. This highlights the importance of understanding the impact of tissue adhesives on peripheral IV survival for patients admitted through the ED. While Bugden found that skin glue reduced IV failures for patients hospitalized from the

ED, patients were only followed for 48 hours. The general consensus is to continue using IVs as long as there is no clinical indication for removal. As the average hospital length of stay in the United States is 4-6 days, it is clear that the 48 hour cutoff is a critical flaw in the analysis and further investigation over a longer time period is urgently needed.

We propose a prospective randomized controlled trial to evaluate peripheral IV failure with ED patients that are hospitalized comparing securement with standard securement plus Adhezion Biomedical SecurePortIV™ to standard securement.

**Specific Aim 1:** Test the prediction that the experimental securement solution of standard dressing plus Adhezion Biomedical SecurePortIV™ will have a lower probability of failure compared to the control standard of care securement.

For Aim 1, an improved survival of the experimental securement solution will be evaluated by functionality of catheter for intravenous therapy prior to patient discharge. The event is failure of functionality identified during follow-up assessment during hospitalization. Duration of dwell and functional failure of the catheter will be employed to estimate catheter survival.

**Specific Aim 2:** Determine the difference in cause-specific IV failure rates between the experimental and control groups. Specific etiologies to be evaluated include dislodgment, infection, phlebitis, and occlusion.

**Specific Aim 3:** Determine the difference in costs associated with the experimental group versus the control group. Cost calculation will include all costs of placement in each group: labor and material.

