**Exclusion Criteria:**

1. Patients with ultrasound-guided IV insertions
2. Alternate site of cannulation
3. Voluntary withdrawal
4. Patients with a non-standard polyurethane dressing
5. Known allergy to cyanoacrylate or formaldehyde

The survival analysis will only be performed on patients that have an IV dwell time greater than 48 hours. Over 85% of patients admitted to a progressive floor have length of stay greater than 48 hours. The sample size calculation reflects an assumed 10 - 15% exclusion rate.

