A tourniquet may be applied as needed. If the patient is actively receiving an infusion, the drip will briefly be halted to evaluate for functionality. Functionality will be assessed with the existing dressing in place. If the catheter is functional and free of any signs of complications, study subjects will be randomized by a computer generated 1:1 envelope system to either the control group: polyurethane dressing + clear tape or the experimental group: polyurethane dressing + clear tape + tissue adhesive. If the IV is not functional, a new catheter will be inserted in a new location, documented, and patient continues in the study. For the control group, the polyurethane dressing will be gently removed. Dressing will be removed carefully to minimize any potential dislodgments or skin injury. The site will be evaluated for oozing or blood and as needed cleaned with sterile gauze. Once the site is completely dry, a new polyurethane dressing will be applied and reinforced with tape in a standard fashion. See Appendix A for pictures depicting standard dressing application with tape. Once securement is complete, functionality will be reassessed per protocol above. For the experimental group, the existing securement will be gently removed. The site will be evaluated for oozing or blood and as needed cleaned with sterile gauze. Once the site is completely dry, the tissue adhesive will be applied per directions in Appendix B. A new standard polyurethane dressing will be applied and tape will be applied per the standard approach. Once securement is complete, functionality will be reassessed per protocol above. The time of the new dressing application will be noted as time zero. Catheter dwell time will begin at this point.

Additional data variables collected at the initial assessment include: demographics such as age, sex, INR > 1.5, platelets < 50, insertion site details, hours from insertion to recruitment, inserter credentials.

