### ***Follow-up Assessment:***

After initial assessment, the catheter will be assessed by the research team every 24 +/- 5 hours as long as the patient is hospitalized up to 7 days or 168 hours. At each follow up interval the researcher notes the date/time of evaluation and assesses for any signs and symptoms of complications and functionality of the device. A catheter is functional if the IV flushes without resistance. Catheters will be assessed daily for signs and symptoms of complications. See Appendix C for details regarding the assessment for complications. Any signs or symptoms of complications or lack of functionality will be reported to the patient's primary care team so that management of the IV catheter can be addressed. If the catheter and adhesive are removed early due to catheter failure or complication, or for patient discharge prior to 7 days a medical adhesive remover may be used.

If the catheter was identified to have any signs or symptoms of complications during follow-up assessment the date and time of observation of the complication will be documented in the data collection tool and the primary team will be notified of the complication. If the catheter was removed prior to the follow-up assessment then the IV removal time and the reason for removal will be obtained through chart review. For all catheters removed due to a complication, re-insertion attempt data will be tracked through the medical record in the nursing section for venous lines and need for reinsertion of the IV or escalation to a midline, PICC, or CVC will be noted. If the patient is discharged prior to the time of follow-up assessment then the time of discharge will be documented and the IV will be presumed functional until time of discharge unless otherwise noted in the chart.

The medication administration record will be queried for all medications given through each catheter with specific attention to antibiotics and anticoagulants. Vesicants/irritants that are generally given via central line or considered caustic to the vessel will be noted in both groups. Number of doses will be recorded. See Appendix D for full list of non-neoplastic vesicants.

Additional data gathered by research staff on follow-up evaluation includes: dwell time in days/hours, hospital length of stay, and number of peripheral IVs for duration of stay.

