Appendix E represents the data collection documentation tool for all catheter follow-ups.

## **Statistical Rationale and Analysis Plan:**

### ***Sample Size and Power Analysis***

For this randomly allocated two-groups experiment, the primary outcome is catheter survival associated with securement devices. Sample size calculation is based on primary outcome: composite or all cause premature removal due to complication of the IV catheter. Based on existing literature, the maximum mean failure rate across major investigations is 25% which functions as the estimated failure rate of the standard of care group. Assuming a minimum difference of 10% needed for prompting a change in practice and based on existing literature, the experimental group (standard of care plus tissue adhesive) is hypothesized to have a composite failure rate of 15%. 154 subjects per group for a total sample size of 308 subjects is the minimum recommendation assuming a 10% dropout rate. To account for a larger dropout percentage, 350 patients or 175 subjects per group is the final sample size to provide 80% power to detect a significant effect.

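### The 48-hour dwell restriction removes early catheter failures from the primary survival analysis and conflicts with the discharge rule in Appendix E

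*Combined protocol and SAP*

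**What the plan says.** The restriction stands under Exclusion Criteria: "The survival analysis will only be performed on patients that have an IV dwell time greater than 48 hours". The reason follows at once: "Over 85% of patients admitted to a progressive floor have length of stay greater than 48 hours", and then "The sample size calculation reflects an assumed 10 - 15% exclusion rate". The restriction concerns catheter dwell; the reason concerns hospital stay.

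The dwell clock is fixed under Initial Assessment, after the randomisation step: "The time of the new dressing application will be noted as time zero. Catheter dwell time will begin at this point".

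The primary event has no 48 h lower limit in either place where it is described. Specific Aim 1: "The event is failure of functionality identified during follow-up assessment during hospitalization". Sample Size and Power Analysis: "composite or all cause premature removal due to complication of the IV catheter". Follow-up Assessment schedules checks every 24 ± 5 h up to 168 h, so failures in the first two days are looked for and recorded.

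The follow-up form in Appendix E has a different rule. It takes a patient out of the study only for discharge less than 48 h after insertion.

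Statistical Analysis names Cox regression for time-to-event outcomes and logistic regression for binary outcomes. It defines no analysis set.

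**The concern.** A dwell time of 48 h or less can mean that the patient went home, that therapy ended, or that the catheter failed. The third is the outcome. A rule based on dwell alone therefore selects patients after randomisation by whether they have already had the primary event, and the catheters compared are those that survived 48 h. Aim 1 asks about failure up to discharge, and that set cannot answer it.

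Two harms are possible. If the hazard ratio is constant, the estimate stays about right but events and power are lost. If the adhesive works mainly in the first two days, the rule removes the effect itself. The second possibility cannot be dismissed: by the protocol's own account, the earlier emergency department trial of skin glue reported a 10% reduction in failure with only 48 h of follow-up. That does not show that benefit stops at 48 h, but the cited effect arose in the window that this rule discards.

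The conflict with Appendix E matters separately. Two analysts, each following one part of the document, would analyse different patients, and the choice could be made after results are known.

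**Working it through.** **The rules side by side.** Take a catheter dislodged 24 h after the study dressing in a patient who stays seven days.

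| Place | Treatment of this catheter |
|---|---|
| Specific Aim 1; Sample Size and Power Analysis | Primary event |
| Exclusion Criteria | Dwell 24 h, so left out of the survival analysis |
| Appendix E | Not discharged early, so kept |

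The clocks also differ. Appendix E counts from insertion, and enrolment may follow insertion by up to 8 h. Because time zero comes after insertion, anyone discharged less than 48 h from insertion also has dwell below 48 h. The reverse does not hold, so Appendix E is the narrower rule.

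**Inputs.** From the documents: failure 25% vs 15%, 175 per arm, follow-up to 168 h, over 85% staying more than 48 h, significance level 0.05 (two-sided assumed). Assumed, because failure timing is not given: constant hazards reaching 25% and 15% at 168 h.

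**The plan's own figures.** The upper end of the 10–15% allowance equals the short-stay share, 100% − 85% = 15%. The 80% power does not reproduce: the pooled two-proportion formula needs 250 per arm before dropout, and 175 per arm gives 64.9%. That is a separate matter, so the comparisons below start from 64.9%.

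**Failures lost**

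- Hazards: λc = −ln(0.75)/168 and λe = −ln(0.85)/168; ratio ln(0.85)/ln(0.75) = 0.565.
- Failed by 48 h: 1 − 0.75^(48/168) = 7.89%; 1 − 0.85^(48/168) = 4.54%.
- Share of all failures: (0.0789 + 0.0454)/(0.25 + 0.15) = 31%. In numbers, 175 × 0.0789 + 175 × 0.0454 = 13.8 + 7.9 = 21.7 of 70, if nobody is discharged early.
- Failure after 48 h among those kept: (0.25 − 0.0789)/0.9211 = 18.6%; (0.15 − 0.0454)/0.9546 = 11.0%. The contrast falls from 10 to 7.6 points.

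**Two-proportion power**

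Power = Φ{[|p1 − p2| − 1.96·√(p̄(1 − p̄)(1/n1 + 1/n2))] / √(p1(1 − p1)/n1 + p2(1 − p2)/n2)}

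- All patients, 175 per arm: (0.100 − 1.96 × 0.04276)/0.04243 = 0.38, so 64.9%.
- Dwell over 48 h, 161.2 and 167.1 kept: (0.0761 − 1.96 × 0.0391)/0.0390 = −0.01, so 49.5%.

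| Discharge loss in both sets | All | Dwell > 48 h |
|---|---|---|
| None | 64.9% | 49.5% |
| 10% | 60.3% | 45.5% |
| 15% | 57.8% | 43.5% |

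If the 25% and 15% are instead reached at 96 h, about 37 of 70 failures are lost and power with no discharge loss is 36.4%.

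**Share excluded.** With 15% short stays: 1 − 0.85 × (0.9211 + 0.9546)/2 = 20.3%, against the 10–15% allowed.

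**Log-rank simulation.** Constant hazards as above, 175 per arm, log-normal stay (assumed median 108 h, 85% above 48 h) timed from time zero, censoring at discharge or 168 h, 10,000 replicates. Power counts results favouring the adhesive at two-sided 5%. The Appendix E column ignores the gap of up to 8 h between its clock and time zero.

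| | All randomised | Appendix E rule | Dwell rule |
|---|---|---|---|
| Power | 48% | 46% | 30% |
| Mean events | 46.5 | 44.2 | 25.7 |
| Excluded | 0% | 15% | 20% |
| Hazard ratio | 0.565 | 0.565 | 0.567 |

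With median stay of 96 h the powers are 47% (all) and 27% (dwell rule); with 144 h, 52% and 33%.

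**Early-concentrated benefit (assumed).** Failure by 48 h is 15% vs 5%, with equal hazards afterwards. With a later hazard of −ln(0.75/0.85)/120, all randomised patients give hazard ratio 0.50 and power 69%. With later hazard λc the figures are 0.575 and 60%. Under the dwell rule both versions give hazard ratio 1.00 and power of about 2%.

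**The case against.** The strongest reply is that only short stays were meant. The two sentences after the restriction speak of length of stay and a 10–15% loss, which fits a discharge rule excluding 15% better than a dwell rule excluding 20%. Appendix E, where exclusion is put into practice, refers to discharge. On that reading, under constant hazards, the cost is about 2 points of power and the hazard ratio does not change. This may well be the intent. The operative sentence still says dwell, however, and nothing in the document gives Appendix E precedence.

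It can also be said that only the survival analysis is restricted, so early failures could enter a logistic regression or Aim 2. That is true, but catheter survival is the primary outcome, and the logistic model does not put these failures back into it.

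The simulated powers deserve caution. Taking 25% and 15% as 168 h risks and then censoring at discharge gives observed failure of only 16.7% vs 9.9%. That is why the log-rank powers sit below the two-proportion powers; the two sets of figures describe different calibrations. Recalibrated so that observed failure is 25% vs 15%, power is about 66–67% for all randomised, 64–65% under Appendix E and 43–44% under the dwell rule. The absolute levels rise, and the loss from the dwell rule widens to about 23 points. The protocol's 4–6 days is an average, whereas 4–6 days was used here as the median, so the longer-stay case is generous.

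The early-benefit scenario gives a later hazard ratio of 1 by construction. It shows what could be missed and is not evidence that it will be.

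**Conclusion.** The concern holds on the text alone. As written, the primary survival analysis leaves out failures that the plan itself defines as primary events, and it does so by a post-randomisation rule tied to the outcome. Exclusion Criteria and Appendix E cannot both be followed.

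The size depends on failure timing, which the documents do not give. Under constant hazards the dwell rule costs about 15 points of two-proportion power, or about 18 to 23 points of log-rank power depending on calibration, without biasing the hazard ratio. If the benefit is confined to the first 48 h, the effect disappears from the analysis. If a short-stay rule was intended, the loss under constant hazards is small, but the sentence still has to be corrected because it says something else. This must be fixed before analysis.

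**What to change.** Replace the restriction under Exclusion Criteria with wording such as: *The primary Cox analysis includes all randomised patients by assigned group, from time zero. Failure at or before 48 h is an event. Functional catheters are censored at discharge, elective removal or 168 h.*

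In Appendix E, replace removal of early-discharged patients from the study with censoring at discharge. Follow-up Assessment already supports this: for a patient discharged before the next check, "the IV will be presumed functional until time of discharge unless otherwise noted in the chart". For a catheter removed before a check, "the IV removal time and the reason for removal will be obtained through chart review".

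Keep the over-48 h set, if wanted, as a secondary landmark analysis labelled as such. Counting early failures is the essential step. Keeping early discharges adds about 2 points of power under constant hazards and preserves the randomised set.

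The cost is a change of wording in two places, with no new data. Some short, early-censored follow-ups will enter the primary set. Two details should be settled in the same revision: how to treat a catheter lost between randomisation and the new dressing, and which removal reasons on the form (such as removed by patient, site changed, other) count as events. The shortfall against the stated 80% power is a separate problem that this change does not resolve.

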**Study Procedure:**

***Initial Assessment:***

Patients admitted from the ED to a progressive floor are eligible participants. Research staff will approach a convenience sample of patients admitted to the progressive floors based on screening of the electronic medical record. These patients are admitted to a progressive floor but approached by research staff when physically in the emergency department waiting for a room assignment. The principal investigator may also choose to include additional patients admitted to non-progressive inpatient units. The principal investigator will inform the research staff when such cases arise. Similar to other study subjects, these patients will be approached in the Emergency Department. If the patient agrees to participate in the

trial, the study subject will be consented by the research staff. Research staff will confirm functionality of the existing IV previously placed by ED staff. The assessment will include observing for blood return into the tubing upon aspiration and/or unobstructed flush with a minimum of 1-2 ml of normal saline. Staff will also observe the site for any signs of redness or tenderness.

A tourniquet may be applied as needed. If the patient is actively receiving an infusion, the drip will briefly be halted to evaluate for functionality. Functionality will be assessed with the existing dressing in place. If the catheter is functional and free of any signs of complications, study subjects will be randomized by a computer generated 1:1 envelope system to either the control group: polyurethane dressing + clear tape or the experimental group: polyurethane dressing + clear tape + tissue adhesive. If the IV is not functional, a new catheter will be inserted in a new location, documented, and patient continues in the study. For the control group, the polyurethane dressing will be gently removed. Dressing will be removed carefully to minimize any potential dislodgments or skin injury. The site will be evaluated for oozing or blood and as needed cleaned with sterile gauze. Once the site is completely dry, a new polyurethane dressing will be applied and reinforced with tape in a standard fashion. See Appendix A for pictures depicting standard dressing application with tape. Once securement is complete, functionality will be reassessed per protocol above. For the experimental group, the existing securement will be gently removed. The site will be evaluated for oozing or blood and as needed cleaned with sterile gauze. Once the site is completely dry, the tissue adhesive will be applied per directions in Appendix B. A new standard polyurethane dressing will be applied and tape will be applied per the standard approach. Once securement is complete, functionality will be reassessed per protocol above. The time of the new dressing application will be noted as time zero. Catheter dwell time will begin at this point.

Additional data variables collected at the initial assessment include: demographics such as age, sex, INR > 1.5, platelets < 50, insertion site details, hours from insertion to recruitment, inserter credentials.

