## Appendix B: Tissue Adhesive Application Instructions

|  |  |
|--|--|
| 
Point the tip towards the ceiling and away from the patient. Press the bottom of the applicator upward.
   |  |
| 
Invert the applicator and gently squeeze the ridges to initiate adhesive flow. Place 1-2 drops of adhesive at the catheter-skin junction.
 
Allow each drop of glue to “set-up” for a few seconds before adding the next drop.
 
Make sure the tissue adhesive is surrounding the entire circumference of the catheter.
 |  |
| 
Place an additional 1-2 drops of adhesive under the catheter hub/extension set connection.
 
Apply gentle pressure for 30 seconds to ensure securement between the catheter and the skin surface.
  |  |

|  |   |
|--|---|
| 
As desired, the remaining adhesive can be spread out beyond the area of the catheter to increase dressing adherence.
 |  |
| 
After application of SecurePortIV, a transparent film dressing should be applied per facility protocol.
                     |  |

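### A catheter lost between randomisation and the new dressing is not scored, and a failed post-securement recheck has no stated outcome

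*Combined protocol and SAP*

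**What the plan says.** All of this is in the combined protocol and SAP.

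- **Randomisation** (Initial Assessment). Function is checked with the original dressing on. Then: "If the catheter is functional and free of any signs of complications, study subjects will be randomized by a computer generated 1:1 envelope system". The next sentence reads: "If the IV is not functional, a new catheter will be inserted in a new location, documented, and patient continues in the study".
- **Securement** (Initial Assessment, Appendix B). The existing dressing is taken off in both arms. In the experimental arm only, adhesive is placed where the catheter enters the skin and beneath the hub, followed by this step: "Apply gentle pressure for 30 seconds to ensure securement between the catheter and the skin surface". Both arms then get a new dressing and tape.
- **Recheck** (Initial Assessment, stated for each arm): "Once securement is complete, functionality will be reassessed per protocol above". No consequence of failing it is given.
- **Clock** (Initial Assessment): "The time of the new dressing application will be noted as time zero. Catheter dwell time will begin at this point".
- **Event** (Specific Aim 1): "The event is failure of functionality identified during follow-up assessment during hospitalization". The Follow-up Assessment section starts follow-up once the initial assessment is over.
- **Other outcome wording.** Follow-up Assessment takes the time and reason of removal from the chart when a catheter is out before a follow-up visit. Sample Size and Power Analysis describes the primary outcome as all-cause early removal for a complication, without tying it to a visit.
- **Analysis set** (text under Exclusion Criteria). The survival analysis is confined to patients whose catheter dwell exceeds 48 hours.

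**The concern.** Aim 1 compares two securement strategies, and applying the strategy is part of it. The only step that differs between the arms falls after allocation and before the clock starts. If a catheter is lost there, the stated rules do not charge the loss to the arm in which it happened, whereas any later benefit of the adhesive is counted.

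Two things are at stake. First, if loss during securement differed between arms, the comparison would no longer be the one that randomisation protects, and the estimated difference would shift. Second, with no rule, staff must improvise. One could record a failure, another could leave the patient out, and another could place a new catheter and follow that one. The last course would put into the analysis a catheter that was not the one found functional at randomisation.

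**Working it through.** **Step 1: trace a lost catheter through the rules.**

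| When the catheter is lost | Relative to time zero | Event under Specific Aim 1? | Other route to being counted | In the survival analysis (dwell over 48 hours)? |
|---|---|---|---|---|
| After randomisation, before the new dressing | Before | No; not found at follow-up | None explicit; it has no dwell time | No |
| At the post-securement recheck | At or just after | Not as worded; the recheck is part of the initial assessment | Possibly chart review, the Day 1 row of Appendix E, or the all-cause removal wording | No; dwell is close to zero |
| At a later follow-up visit | After | Yes | Not needed | Only if dwell exceeds 48 hours |

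The first row is a definite gap. The second is an ambiguity. In both rows the 48-hour restriction removes the randomised catheter from the survival analysis even if the loss is recorded. If a replacement were followed instead, the patient could re-enter that analysis through the replacement's dwell time. No 48-hour limit is stated for the binary (logistic) analyses, so there a recorded recheck failure could count.

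**Step 2: illustrate the size.** Inputs from Sample Size and Power Analysis: failure of 25% (control) and 15% (experimental), 175 patients per arm. The plan's own difference reproduces: 25 − 15 = 10 points. The documents give no loss rate during securement, so every loss rate below is assumed.

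Let qC and qE be the proportions lost during securement in the control and experimental arms, and let the planned rates apply to the catheters then followed. Counted from randomisation:

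- control failure = qC + (1 − qC) × 0.25
- experimental failure = qE + (1 − qE) × 0.15
- difference = 0.10 + 0.75 qC − 0.85 qE

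The trial as written would report about 0.10 throughout, so the overstatement is 0.85 qE − 0.75 qC.

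| Assumed loss | Catheters of 175, per affected arm | Control | Experimental | Difference (points) | Overstatement (points) |
|---|---|---|---|---|---|
| 1%, experimental only | 1.75 | 25% | 15.85% | 9.15 | 0.85 |
| 2%, experimental only | 3.5 | 25% | 16.70% | 8.30 | 1.70 |
| 3%, experimental only | 5.25 | 25% | 17.55% | 7.45 | 2.55 |
| 1%, both arms | 1.75 | 25.75% | 15.85% | 9.90 | 0.10 |
| 3%, both arms | 5.25 | 27.25% | 17.55% | 9.70 | 0.30 |

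Equal loss hardly moves the difference, although both failure rates are understated. Loss that differs by arm is what matters. Excess loss in the control arm would bias the other way: 1% there alone understates the benefit by 0.75 points. These figures treat failure as a simple proportion of all randomised patients; they do not describe the set limited to dwell over 48 hours.

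**The case against.** Three parts of the case against this point stand.

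- **The replacement rule.** A reader might infer that replace-and-continue governs the securement step, so that a catheter lost there is bound to be swapped and can never be counted. The documents do not support that. The sentence directly follows the randomisation condition and precedes any dressing removal, so it is most naturally the other branch of the pre-randomisation check. The recheck's reference to the protocol above may mean only the test method (blood return or flush). On that reading, no rule at all covers a post-randomisation loss, and the gap remains.
- **Other capture routes.** A failure at the recheck falls at or after time zero. Chart review or the all-cause removal outcome might pick it up.
- **Mechanism.** A reader might also infer that the protocol admits that applying adhesive can dislodge the catheter. Its only warning is "Dressing will be removed carefully to minimize any potential dislodgments or skin injury". That concerns dressing removal, which both arms undergo, and it stands in the control-arm text. Nothing in the documents says adhesive application causes loss, and enrolling staff are to be proficient before enrolment begins.

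It can also be argued that starting dwell at completed securement, in the same way in both arms, is a coherent way to measure how well a dressing holds. That is fair for measuring dwell. It does not settle what happens to a randomised catheter that never reaches that point.

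**Conclusion.** The point holds, at minor severity. Under the stated rules, a catheter lost between randomisation and the new dressing is not scored. A failure at the post-securement recheck has no stated outcome, though it might be captured by other routes. The documents do not show that the trial is biased towards the adhesive: no loss rate is given, and arm-specific loss is a possibility rather than a finding. The effect is of unknown and probably small size and matters mainly if loss differs by arm. At an assumed 1% to 2% excess in the experimental arm, about 2 to 4 of 175 catheters, the benefit would be overstated by about 0.9 to 1.7 of the planned 10 points. That rests on the planned 25% and 15% applying to the catheters actually followed. The 48-hour dwell restriction is the larger obstacle, because it would drop these losses from the survival analysis even if they were recorded.

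**What to change.** For outcome definition and analysis only:

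1. In Initial Assessment and Specific Aim 1, fix the index catheter and start outcome counting at randomisation (envelope opened) in both arms.
2. Score loss during securement, or non-function at the post-securement recheck, as a failure in the assigned arm, and report these failures by arm.
3. State that, for analysis, the replace-and-continue sentence applies only before randomisation, and that a catheter placed after randomisation is recorded but not analysed as the study catheter.
4. Reconcile the 48-hour dwell restriction under Exclusion Criteria so that it does not remove these failures from the survival analysis. Without this, items 1 and 2 would not reach that analysis.

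The cost is protocol wording and one extra time stamp; Appendix E already has a failed code and a rescue-device column. No extra patients or procedures are needed. The downside is that a few very early events may be added, which could make the experimental arm look slightly less favourable.
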